## **Abbreviations**

ACP Advance Care Planning

AD Advance directives

ADBI After Death Bereavement Interview

AE Adverse Event

CCCP Care consistency with care preferences

CI Confidence interval

CPR Cardiopulmonary resuscitation

cRCT Cluster randomized trial

CRF Case Record Form

DC1 Data collection 1
DC2 Data collection 2

EFS Evalued for Safety Set

HADS Hospital Anxiety and Depression Score

IEC Independent Ethics Committee

IQR Interquartile range

IRB Institutional Review Board

IRR Incidence rate ratio

ITT Intention-to-treat

NH Nursing home

OR Odds ratio

POLST-E Physician or patient/proxy order for life sustaining treatment in emergencies

PP Per Protocol population

SD Standard deviation

SAP Statistical Analysis Plan SDM Shared decision making

3CP Care consistency with care preferences

## 1. Introduction

This Statistical Analysis Plan (SAP) is based on the study protocol version 1.0 of May 22, 2022 and follows the guideline for statistical analysis plans [1].

Some elements of the statistical methods and of the study design have already been described in the study protocol [2]. This Statistical Analysis Plan (SAP) aims to further specify the procedures and statistical methods to be applied during the final analysis of the study data.

This SAP is finalized and published before unblinding of the outcome assessors (Biometry, Hamburg) took place.

### 1.1 Background and rationale

Advance Care Planning (ACP) for residents of nursing homes (NHs) has recently been covered by German sickness funds. However, clinical effects of ACP have not been studied in Germany yet. The purpose of this study is to investigate whether implementing a comprehensive ACP program improves care consistency with care preferences of NH residents. The aim is to increase consistency between medical treatments provided and the respective patient preferences, and to reduce the corresponding emotional burden for health care proxies and staff. In addition, place of death should more often be the NH, i.e. at home, rather than the hospital, consistent with the residents' wishes. The complex ACP intervention comprises training of professional ACP facilitators, supporting organizational development in NHs and other relevant institutions, and moderating regional change management among a network of all related health care institutions and players.

### 1.2 Objectives

The goal of the multicenter BEVOR study is to evaluate the effectiveness of a structured advance care planning (ACP) program in NH residents regarding the reduction of unwanted medical interventions, notably hospital admissions, as compared to a control group. Conversely, the rate of residents whose treatment preferences are known and honored should be increased.

In the following, the time point of baseline measurement is defined as t0, of the end of the run-in phase of the intervention as t1, and of succeeding 12-months follow-up as t2. For more details, see section 2.7.

Researchers will take two independent approaches for data collection:

Firstly, participating NHs will provide anonymous pooled data on all their residents which include long-term as well as respite care residents of a defined time period (data collection 1 = DC1), including the hospitalization rate (primary outcome).

If not stated otherwise, data of both groups are used, long-term and respite care residents.

Secondly, a cohort of all long-term residents who have given informed consent (or for whom their health care proxy has given informed consent), their health care proxies and/or relatives, and the

respective nursing staff will be repeatedly surveyed until t2 (or until residents die earlier) (data collection 2 = DC2).

The following primary hypothesis will be tested:

**Primary hypothesis:** Compared to the control group, the structured ACP program reduces the 12-month hospitalization rate of residents of NHs at t2.

### 1.2.1 Primary Outcome

The primary outcome is part of the data collection DC1 and is defined as rate of hospitalizations (long-term care only) per 100 residents per year during the 12-months observation period, compared between intervention group and control group at t2. The rate of hospitalizations per 100 residents per year is defined as the quotient of the number of all hospitalizations in the last 12 months observation period divided by the number of occupied bed days multiplied by 365 (days) and 100 (residents).

### 1.2.2 Secondary Outcomes

The secondary outcomes are as follows, analyzed at t2:

At NH level (DC1):

- 1. number of hospital days (long-term) per 100 residents per past 12 months
- 2. number of hospital stays (long-term) per 100 residents during observation period (without consideration of occupied bed days)
- 3. number of patients with at least one hospitalization per 100 residents per past 12 months
- 4. number of residents who died in the hospital per 100 residents per past 12 months
- 5. number of pre-specified unwanted invasive treatments per 100 residents measured:
  - a. number of residents with feeding tube (PEG) in place (cross-sectional)
  - b. number of residents with PEG in use (cross-sectional)
  - c. number of attempts of cardiopulmonary resuscitation (CPR) per past 12 months
  - d. number of attempts of successful CPR per past 12 months
- 6. number of legal guardians per 100 residents (cross-sectional)
- 7. number of durable powers of attorney (DPOA) per 100 residents (cross-sectional)
- 8. advance directives (ADs)
  - a. number of all advance directives per 100 residents (cross-sectional)
  - b. number of advance directives signed by resident per 100 ADs (cross-sectional)
  - c. number of advance directives last signed in the last 6m per 100 ADs (cross-sectional)
  - d. number of advance directives in long-term care only per 100 ADs (cross-sectional)

- 9. physician or patient/proxy orders for life sustaining treatment in emergencies (POLST-E)
  - a. number of POLST-E per 100 residents (cross-sectional)
  - b. number of POLST-E not signed by resident per 100 POLST-E (cross-sectional)
  - c. number of POLST-E in the last 6m per 100 POLST-E (cross-sectional)
  - d. number of POLST-E with a do-not-hospitalize order per 100 POLST-E (cross-sectional)
  - e. number of POLST-E per 100 residents (long-term care only; cross-sectional)

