### At NH level:

All secondary endpoints are count data.

For the endpoints 1,2, 4 and 5 c. & d., a Poisson Regression model is calculated with the respective number per 100 residents per past 12 months' observation period (from t1 to t2) as dependent variable, group (intervention vs control) as independent variable, number of occupied bed days as offset and the respective baseline rate and region of NHs as covariates.

The treatment effect is presented as incidence rate ratio (IRR) with corresponding 95%-CI and p-value. Marginal estimators (numbers per 100 residents per past 12 -months observation period (from t1 to t2)) with corresponding 95%-CI are given per treatment group.

For the secondary endpoint 3, the number of residents during the observation period before t2 is used as offset variable. The resulting marginal estimators are numbers per 100 residents.

The secondary endpoints 5 a. & b. and 6-7, 8 a. and 9 a. are measured cross-sectional. For these endpoints, a Poisson Regression model is calculated with the respective number as dependent variable, group (intervention vs. control) as independent variable, number of residents as offset and the respective baseline rate and region of NHs as covariates.

The treatment effect is presented as IRR with corresponding 95%-CI and p-value. Marginal estimators (numbers per 100 residents per past 12 -months observation period (from t1 to t2)) with corresponding 95%-CI are given per treatment group.

The secondary endpoints 8 b. - d. and 9 b. - e. are measured cross-sectional, too, but refer to a predefined subgroup.

For these endpoints, a Poisson Regression model is calculated with the respective number as dependent variable, group (intervention vs control) as independent variable and the respective baseline rate and region of NHs as covariates.

For the endpoints 8 b. - d. the number of ADs and for the endpoints 9 b. - e. the number of POLST-Es are set as offset, respectively.

The treatment effect is presented as IRR with corresponding 95%-CI and p-value. Marginal estimators (number per 100 ADs or 100 POLST-Es per past 12 -months observation period (from t1 to t2)) with corresponding 95%-CI are given per treatment group.

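### Endpoint 8d divides long-term-care advance directives by all advance directives, so it measures their mix rather than how common they are in long-term care

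*SAP*

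**What the plan says.** SAP section 1.2.2 lists four AD endpoints at nursing-home level (DC1). 8a is the prevalence measure: "number of all advance directives per 100 residents (cross-sectional". 8b and 8c describe features of the ADs themselves (signed by the resident, signed recently) and are expressed per 100 ADs. 8d is "number of advance directives in long-term care only per 100 ADs (cross-sectional".

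Section 5.1.3, under the NH-level heading, is consistent with this. It says that 8b–d and 9b–e "are measured cross-sectional, too, but refer to a predefined subgroup" and fixes the offset: "For the endpoints 8 b. - d. the number of ADs". Results are given as "Marginal estimators (number per 100 ADs or 100 POLST-Es per past 12 -months observation period (from t1 to t2". For 8a, by contrast, the model has "number of residents as offset and the respective baseline rate and region of NHs as covariates".

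Section 1.2 settles which ADs are meant when nothing is added: "If not stated otherwise, data of both groups are used, long-term and respite care residents". The denominator of 8d is therefore all ADs in the home.

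The corresponding endpoint for emergency orders, 9e, is "number of POLST-E per 100 residents (long-term care only; cross-sectional". Section 1.2.2 names 9e as a key secondary endpoint, yet section 5.1.3 includes it in the group whose offset is the number of POLST-Es.

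**The concern.** 8b and 8c ask what kind of ADs exist, so dividing by ADs suits them. 8d names a resident population instead. Dividing by all ADs turns it into a statement about how ADs split between long-term and respite residents. An intervention that produces more ADs raises numerator and denominator together, and the ratio barely moves.

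The primary outcome is restricted to long-term care, and 9e as defined gives POLST-E prevalence in that population. No DC1 endpoint does so for ADs. 8d would be reported under advance directives with an IRR, confidence interval and p-value. A value near 1 there would carry almost no information about whether the programme increased ADs.

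**Working it through.** The SAP states no figure for 8d, so there is nothing to reproduce.

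**Inputs.** Definition and offset come from sections 1.2.2 and 5.1.3. The respite share *r* and the AD prevalences *pL* (long-term) and *pR* (respite) are assumptions, because the SAP gives none of them. One AD per resident with an AD is assumed for simplicity; the unit of 8d is ADs, not residents who hold one.

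**Formulas.**
- 8d = (1−r)·pL / [(1−r)·pL + r·pR]
- 8a = (1−r)·pL + r·pR

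With the same *r* in both arms, (IRR of 8d) × (IRR of 8a) = the long-term prevalence ratio. What 8a captures, 8d therefore cannot show.

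**Case 1: ADs double in both resident groups.** The factor 2 cancels, so the IRR of 8d is 1.000 for any *r*.

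**Case 2: only long-term prevalence doubles, 30% to 60%; respite stays at 30%.** Example for r = 5%: control 0.95×0.30 / (0.95×0.30 + 0.05×0.30) = 0.950; intervention 0.95×0.60 / (0.95×0.60 + 0.05×0.30) = 0.570/0.585 = 0.974; ratio 1.03. For 8a: 0.585/0.300 = 1.95.

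| r | 8d control → intervention, per 100 ADs | IRR 8d | 8a control → intervention, per 100 residents | IRR 8a | True long-term ratio |
|---|---|---|---|---|---|
| 3% | 97.0 → 98.5 | 1.02 | 30 → 59.1 | 1.97 | 2.0 |
| 5% | 95.0 → 97.4 | 1.03 | 30 → 58.5 | 1.95 | 2.0 |
| 10% | 90.0 → 94.7 | 1.05 | 30 → 57.0 | 1.90 | 2.0 |

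**Wider range.** With equal starting prevalence the IRR of 8d is 1.11 at r = 20% and 1.18 at r = 30%. With unequal starting prevalence (long-term 20%, respite 40%) it is 1.05 at r = 5%, 1.10 at 10% and 1.30 at 30%. All are far from 2.0.

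**Case 3: no effect on ADs, but the mix differs.** If prevalence is equal everywhere and the respite share is 10% in one arm and 5% in the other, 8d gives 0.900/0.950 = 0.95. A modest imbalance in mix moves 8d about as much as a doubling of long-term ADs does.

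**Simulation check.** 22 against 22 homes of 96 residents (the average size in section 2.1), r = 5%, long-term prevalence 40% against 80%, respite 40%, Poisson model with group only (no region or baseline covariate), 500 runs, two-sided 5% level. With the AD offset the mean IRR was 1.03 and no run was significant. With long-term residents as offset the same data gave a mean IRR of 1.99, significant in every run.

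**Other reading of the denominator.** If ADs in 8d meant long-term ADs only, the endpoint would be 100 per 100 in every home.

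**The case against.** For 8d the SAP does not contradict itself. Definition, offset and reporting scale agree, and the endpoint can be read as a description of the pool of ADs, like 8b and 8c. That it was meant as a prevalence is an inference from 9e; no passage says so. This stands. The criticism is that the quantity is uninformative about the intervention, not that two passages conflict.

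A reader might infer that the trial has no usable estimate of AD prevalence in long-term residents, or cannot show an effect on ADs. The SAP does not support that. 8a measures prevalence with residents as offset, and the small respite share that holds 8d near 1 also makes 8a almost equal to long-term prevalence (1.90 to 1.97 against 2.0 above). 31d gives the proportion of residents with any AD in the DC2 cohort, which section 1.2 restricts to consenting long-term residents. With 8a reported alongside, a misreading of 8d is possible rather than likely.

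The parallel with 9e is also only partial: it holds for the definition in section 1.2.2, while section 5.1.3 gives 9e a POLST-E offset. That does not rescue 8d. It shows a second denominator problem in the same rule, and one in a key secondary endpoint.

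**Conclusion.** The point holds as a minor one. As defined and modelled, 8d is the long-term share of ADs. Its IRR is exactly 1 under a proportional rise in both resident groups, and about 1.02 to 1.05 when only long-term prevalence doubles with 3% to 10% respite residents. It reaches 1.30 only in the extreme scenario. These sizes rest on assumed respite shares and prevalences. The exact result of 1 rests only on the definition and on the two arms having the same respite share.

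What is lost is a DC1 estimate of AD prevalence covering all long-term residents, including those who did not consent to DC2. 8d is not a key endpoint, and section 5.1.3 treats secondary outcomes as exploratory, so the primary conclusion is unaffected. The more consequential item in the same paragraph is the offset for 9e, which contradicts that endpoint's definition per 100 residents.

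**What to change.** 1. In section 1.2.2, redefine 8d as the number of ADs in long-term care per 100 long-term-care residents (cross-sectional).
2. In section 5.1.3, take 8d and 9e out of the rule that sets ADs or POLST-Es as offset. Give both the number of long-term residents on the t2 data collection day as offset, compute the baseline-rate covariate on the same denominator at t0, and report per 100 long-term residents. 8b–c and 9b–d keep their present offsets.
3. Confirm that long-term and respite residents were counted separately at t2. Section 4.5 lists resident numbers with both kinds of care, but only for t0 and t1. 9e as defined needs the same count, so this check is required in any case.

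The cost is a few lines of wording and one data check. If the original share is still wanted, it can be kept as a descriptive figure labelled as the long-term share of ADs.

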### At resident level (DC2):

- 10. proportion of treatment decisions in the face of potentially life-threatening events in which the resident's preferences were
  - a. known...
    - i. ... ostensibly, i.e. mere consent or refusal to treatment could be elicited regardless of any level of shared decision making (SDM)) (yes vs. no)
    - ii. .... in the sense of "informed", i.e. consent or refusal to treatment could be elicited and was based on at least the first two of four predefined steps of an SDM process (step 2: "...was informed about available treatment options with benefits and risks") (yes vs. no)
    - iii. ... in the sense of "informed" and "enabled", i.e. additionally at least the 3rd step of the predefined 4-step SDM process was reached ("...was given opportunity to deliberate on the available treatment option") (yes vs. no)
    - iv. ... in the sense of "informed", "enabled" and "empowered", i.e. additionally the 4th step of the predefined 4-step SDM process was reached ("...was encouraged to decide between the available options based on the resident's preferences") (yes vs. no)

## b. AND honored:

- i. "ostensible" preferences (independent of any underlying SDM process) were honored (yes vs. no)
- ii. "informed" preferences (at least the 2nd step of the SDM process was reached) were honored (yes vs. no)
- iii. "enabled" preferences (at least the 3rd step of the predefined 4-step SDM process was reached) were honored (yes vs. no)
- iv. "empowered" preferences (at least the 4th step of the predefined 4-step SDM process was reached) were honored (yes vs. no),

continuously over the 12 months before t2.

- 11. Perception of care consistency in residents deceased during the observation period measured as judgement (Likert Scale 0-10) of
  - a. proxies and

- b. nurses, respectively, whether medical care (F2a) and nursing care (F2b) delivered in the past 3 months before death was consistent with the residents' then care preferences, measured by key items F2a/F2b selected from the After Death Bereaved Family Member Interview (ADBI) and documented continuously over the 12 months before t2.
- 12. Shared decision making and Advance Care Planning in residents deceased during the observation period, observed in the 3 months prior to death, and measured by means of the corresponding sections of an adapted German version of the After Death Bereaved Family Member Interview (ADBI):
  - a. Inform and promote shared decision making (problem score #2)
  - b. Encourage advance care planning (problem score #3)
  - c. Overall Rating Scale for patient focused, family centered care
- 13. number of hospitalizations per 100 residents per last 12 months at t2
- 14. number of total hospital days per 100 residents per last 12 months at t2
- 15. number of visits at hospital outpatient services per 100 residents per last 12 months at t2
- 16. number of attempted CPRs in hospital or EMS per 100 residents per last 12 months at t2
- 17. number of intensive care unit days per 100 residents per last 12 months at t2
- 18. proportion of residents with artificial ventilation in hospital or EMS at t2
- 19. number of invasive ventilation hours in hospital per 100 residents per last 12 months at t2
- 20. proportion of residents with PEG in place at t2
- 21. proportion of residents with newly inserted PEG at t2
- 22. proportion of residents with PEG in use at t2
- 23. mortality rate during the observation period before t2
- 24. place of death (nursing home vs. others) during the observation period before t2
- 25. number of EMS transports per 100 residents per last 12 months at t2
- 26. number of general practitioner visits per 100 residents per last 12 months at t2
- 27. number of referrals to specialists per 100 residents per last 12 months at t2
- 28. proportion of residents who received at least 1 antibiotic at t2
- 29. proportion of residents with legal guardian at t2
- 30. quality of life: residents capable of self-rating use WHO-QoL German Version; residents incapable of self-rating use QUALIDEM at t2
- 31. Process parameters measuring the effect of ACP at t2:
  - a. proportion of residents with advance care plans signed by facilitators, and/or physicians and/or representatives
  - b. proportion of residents with durable power of attorney
  - c. proportion of residents with POLST-E
  - d. proportion of residents with any ADs

BEVOR // UKE 2023

- e. proportion of ADs signed by resident
- f. proportion of residents with AD-by proxy
- g. proportion of residents with POLST-E
- 32. Anxiety, depression and trauma among bereaved relatives at t2:
  - a. Scoring on Revised Impact of Event Scale (IES-R): min. 0 pts, max. 88 pts., higher score indicates higher impact (trauma)
  - b. Scoring in German version of Hospital Anxiety and Depression Score (HADS-D): min. 0, max. 14, higher score indicates higher degrees of anxiety and depression

Key secondary endpoints are 9e, 10a ii and 10b ii. This choice is informed by blinded baseline analyses.

## 1.2.3 Specific outcome definitions

In the following, the calculation rules for specific outcomes are described on the basis of the corresponding questionnaires:

### o ADBI

Referring to outcome 12, for the calculation of problem score #2 (12a), the items C1a, C1b, C1c, C1c(a), D19, D26a, D27a, D28a and E1 are used. The calculation of problem score #3 (12b) is done from a medical (items D2a, D3a, D4a, D4b) and nursing (D2b, D3b, D4c, D4d) perspective. The Overall Rating Scale (12c) is calculated using items F1-F6.

In each case, the score is calculated as sum of the items. The category "I don't know" is considered a missing value. For problem score #2, up to 2 missing values are allowed and replaced by the mean of the resulting items. For problem score #3, up to 1 missing value per item in each perspective is allowed and replaced by the mean of the resulting items. For the overall rating scale, up to 1 missing value is allowed and replaced by the mean value of the resulting items. In case of more missing items the respective score is missing.

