### At resident level:

All analyses relating to the residents of NHs are performed within a framework of multi-level models.

The secondary endpoints 13. – 17., 19. and 25. – 27. are count data. For these endpoints, a mixed Poisson regression model will be calculated with the corresponding number as dependent variable, realized follow-up time as offset, group (intervention vs. control) as fixed effects, the particular baseline measurement as covariate and region NHs and respective NH as nested random intercepts. The treatment effect is presented as IRR with corresponding 95%-CI and p-value. Marginal estimators (numbers per 100 residents per past 12 -months observation period (from t1 to t2)) with corresponding 95%-CI are given per treatment group.

The secondary endpoints 18., 20. - 24., 28. - 29. and 31 are outcome variables with levels 1 = ``yes'' and 0 = ``no'', i.e. binary outcomes. The secondary endpoint place of death (nursing homes vs. others) is also binary.

For binary outcomes, a mixed logistic regression model will be calculated, taking into account the respective binary outcome as dependent variable, group (intervention vs. control) as fixed effect, the particular baseline measurement as covariate and region of NHs and NH as nested random intercept. The treatment effect is presented as odds ratio (OR) with corresponding 95%-CI and p-value. Marginal estimators (proportions of residents at t2) with corresponding 95%-CI are given per treatment group.

The secondary endpoints 11 a. & b. and 12 are continuous and compared between intervention and control group at t2.

A linear mixed model will be calculated including the respective outcome at t2 as dependent variable, group (intervention vs. control) as fixed effects and region of NHs and NH as nested random intercept.

The treatment effect is presented as mean difference with corresponding 95%-CI and p-value. Marginal estimators with corresponding 95%-CI are given per treatment group.

The secondary outcomes 30. and 32 b. are continuous and compared between intervention and control group as change from baseline at t2.

A linear mixed model will be calculated including change from baseline (t2-t0) as dependent variable, group (intervention vs. control) as fixed effects, the respective baseline value (t0) as covariate and region of NHs and NH as nested random intercept.

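### The missing-item limit for ADBI problem score #3 is set per item, so as written it cannot be exceeded; a limit per perspective was probably meant

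*SAP*

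**What the plan says.** SAP section 1.2.3 (ADBI) defines endpoint 12b: "The calculation of problem score #3 (12b) is done from a medical (items D2a, D3a, D4a, D4b) and nursing (D2b, D3b, D4c, D4d) perspective". That is four items per perspective. Scoring is by addition: "In each case, the score is calculated as sum of the items". An answer of not knowing is treated as absent: "The category 'I don't know' is considered a missing value".

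The limits on missing answers follow. For score #2, which lists nine items: "For problem score #2, up to 2 missing values are allowed". For score #3: "For problem score #3, up to 1 missing value per item in each perspective is allowed". The overall rating scale (F1 to F6) may have one missing value. In all three cases a permitted gap is "replaced by the mean of the resulting items". The paragraph closes with: "In case of more missing items the respective score is missing".

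On the analysis, section 5.1.3 says: "The secondary endpoints 11 a. & b. and 12 are continuous and compared between intervention and control group at t2". The model is a linear mixed model and the effect is a mean difference.

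**The concern.** A limit on missing answers has to be one that some records break. Here the limit counts missing values within a single item, and a single item has only one value per respondent. The rule therefore admits every record, including one with no answers, for which there is no mean to insert.

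At stake is which 12b scores enter the analysis. Two programmers could apply the paragraph differently and obtain different data sets, and the choice might fall after unblinding. Because the score is a sum, a perspective with one answer x would be scored x + 3x = 4x and would enter the model as one observation, like a fully answered one. Informants report on the last three months of a deceased resident's life, so answers of not knowing are plausible.

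**Working it through.** **Inputs from the SAP (section 1.2.3, ADBI).** Four items per perspective; sum score; gaps filled with the mean of the answered items; not knowing counts as missing.

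**Input not in the SAP.** The probability q that an item is missing. I take q = 10%, 20% and 30%, independent across items. The plan has no figure of its own on this point to reproduce.

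**Step 1: three readings, over the 2^4 = 16 patterns of answered and missing items in one perspective.**

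- A, literal: each of the four items may be missing. A score can be computed in 15 of 16 patterns, on as little as one answer. It fails only when all four are missing: q^4.
- B, item means the question D2, D3 or D4: only D4 has two parts within a perspective, so only the loss of both D4 parts breaks the limit: q^2. A score can be computed in 12 of 16 patterns, again on as little as one answer.
- C, one missing item per perspective: 5 of 16 patterns are scored, always on at least three answers. The score is missing with probability 1 − (1−q)^4 − 4q(1−q)^3.

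| q | A: score missing | B: score missing | C: score missing |
|---|---|---|---|
| 10% | 0.01% | 1% | 1 − 0.6561 − 0.2916 = 5.2% |
| 20% | 0.16% | 4% | 1 − 0.4096 − 0.4096 = 18.1% |
| 30% | 0.81% | 9% | 1 − 0.2401 − 0.4116 = 34.8% |

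The share that A scores and C does not is the difference between the columns: 5.2%, 17.9% and 34.0%. Scores resting on a single answer under A have probability 4q^3(1−q): 0.36%, 2.6% and 7.6%.

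**Step 2: which reading fits the rest of section 1.2.3.** Score #2 allows 2 missing of 9, the overall rating 1 of 6, WHO-QoL one per subscale and HADS-D one per subscale. All of these count missing items per score or subscale. Only score #3 counts per item. Reading C matches the pattern and is the only one of the three that requires most of the answers.

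**Step 3: effect on a group mean.** This needs assumptions that the SAP does not supply: 0/1 items, a threshold of 0.25 on a normal latent scale, latent correlation 0.3, missingness unrelated to the answers, and clustering ignored. The item variance is then v = 0.401 × 0.599 = 0.240 and the covariance c = 0.046. The complete score has variance 4v + 12c = 1.51 (SD 1.23).

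With k items answered, the filled-in score is four times the mean of those k. Its expectation does not depend on k, so there is no mean bias. Its variance is 16[v/k + (k−1)c/k]: 1.51, 1.77, 2.29 and 3.84 for k = 4, 3, 2 and 1.

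Let P_k be the binomial probability of k answers and V_k that variance. The standard error times the square root of the number interviewed is √(Σ P_k V_k) / Σ P_k, summed over the values of k that are scored:

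| q | Reading A (k = 1 to 4) | Reading C (k = 3, 4) | Increase |
|---|---|---|---|
| 10% | 1.278 | 1.296 | about 1% |
| 20% | 1.342 | 1.416 | about 5% |
| 30% | 1.422 | 1.604 | about 13% |

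**The case against.** The strongest reply is that nobody would apply the literal rule. The closing sentence of the paragraph presupposes a limit that can be exceeded, the neighbouring rules show the pattern, and a programmer who reads the whole paragraph would probably allow one missing item per perspective. This stands as far as intent goes. A reader might infer that the plan means to score 12b on single answers and almost never to set it to missing. The SAP does not support that as its intended rule; it is only what the wording permits. But intent has to be guessed here, and reading B, which keeps the words per item, still admits single-answer scores.

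The second reply is that even the literal rule need not harm the comparison. A reader might point to the error in individual scores: in a simulation on the assumptions of Step 3, the root mean squared error is 0.51, 0.88 and 1.53 points with one, two and three items missing. Those are errors in single records. Endpoint 12 is compared as a mean difference, and on the same assumptions the mean is unbiased and the literal rule is slightly the more precise. This stands.

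A reader might also infer that trained homes give fewer answers of not knowing, so that the distortion differs by arm. The SAP gives no such rate, overall or by arm, and under reading C any difference between arms would instead select respondents differently. That inference is not supported.

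**Conclusion.** The scoring rule for problem score #3 is defective as written. Taken literally, its limit cannot be exceeded, the cut-off sentence is empty for this score, and the all-missing case has no defined value. Reading item as a question block does not repair it. One missing item per perspective was probably meant. The SAP also does not say whether the two perspectives yield one 12b score or two.

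The consequence is an analysed set that depends on the reading: at an assumed 20% item-missing rate, 0.16%, 4% or 18% of perspective scores are set to missing. The missing rates and their independence are assumptions; the defect in the wording is not. No bias in the group comparison is shown. Endpoint 12b is not among the key secondary endpoints (section 1.2.2), and section 5.1.3 treats secondary outcomes as exploratory. The severity is minor.

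**What to change.** Replace the sentence for score #3 with wording to this effect: for problem score #3, one of the four items in a perspective may be missing and takes the mean of the other three; with two or more missing, that perspective's score is missing. In the same edit, state whether 12b is reported as two scores, medical and nursing, or combined into one, and if combined, how.

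The cost is one or two sentences in the SAP and the matching scoring syntax. The price in data is fewer analysable 12b scores and, if items are exchangeable and missing at random, the somewhat larger standard error shown above. If the trial team prefers to keep more records, a looser limit can be defended, provided that it is stated as a number of items per perspective and fixed before unblinding.
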